**Table 4.1-4 Selected CYP2D6 Inhibitors and CYP3A4 Inhibitors and Inducers Prohibited During the Trial**

| Selected CYP2D6 Inhibitors    |                           |
|-------------------------------|---------------------------|
| Celecoxib                     | Hydroxyzine               |
| Chloroquine                   | Methadone                 |
| Chlorpheniramine              | Moclobemide               |
| Clemastine                    | Paroxetine                |
| Clomipramine                  | Pyrilamine                |
| Diphenhydramine               | Quinidine                 |
| Fluoxetine                    | Terbinafine               |
| Halofantrine                  | Tripeplennamine           |
| Selected CYP3A4 Inhibitors    |                           |
| Amiodarone                    | Fluvoxamine               |
| Amprenavir                    | Indinavir                 |
| Aprepitant                    | Itraconazole              |
| Chloramphenicol               | Ketoconazole              |
| Cimetidine                    | Nefazodone                |
| Clarithromycin                | Nelfinavir                |
| Clotrimazole (if used orally) | Quinupristin/Dalfopristin |
| Delavirdine                   | Ritonavir                 |
| Diltiazem                     | Saquinavir                |
| Erythromycin                  | Troleandomycin            |

| Table 4.1-4 Selected CYP2D6 Inhibitors and CYP3A4 Inhibitors and Inducers Prohibited During the Trial |                 |
|--|-----------------|
| Selected CYP2D6 Inhibitors  |                 |
| Fluconazole  | Verapamil       |
| Selected CYP3A4 Inducers  |                 |
| Carbamazepine  | Phenytoin       |
| Dexamethasone  | Primidone       |
| Efavirenz  | Rifampin        |
| Nevirapine   | St. John's Wort |
| Oxcarbazepine  | Troglitazone    |
| Phenobarbital  |                 |

## 4.2 Other Restrictions

### 4.2.1 Restricted Therapies and Precautions

Any history of electroconvulsive therapy is exclusionary.

Use of intramuscular (IM) benzodiazepines is prohibited throughout the trial. Short-term use of specific oral benzodiazepines is allowed during the trial for the control of agitation or insomnia as shown in [Table 4.1-3](#). Short-acting benzodiazepines (ie, lorazepam or oxazepam) are to be used whenever possible. In countries or institutions where no short-acting benzodiazepines are commercially available, use of oral diazepam or oral clonazepam may be acceptable if prior authorization is obtained from the medical monitor. The investigator should contact the medical monitor to discuss any subject who requires frequent use of a benzodiazepine for agitation or insomnia beyond the first 2 weeks of the trial.

Non-benzodiazepine sleep aids (ie, zolpidem, zaleplon, zopiclone, and eszopiclone only) are permitted for the treatment of insomnia, but not on the same day as administration of a benzodiazepine, regardless of indication. For the non-benzodiazepine sleep aids, sites should only utilize 1 of the listed medications that are approved for this indication in their respective countries and the country-specific prescribing information is to be used to determine the maximum allowable daily dose for the treatment of insomnia.

Anticholinergics are permitted for the treatment of EPS up to a maximum of 4 mg/day benztrapine or its equivalent and propranolol is permitted for akathisia or tremor up to a maximum of 60 mg/day. Subjects receiving a stable dose of propranolol for other conditions at entry into Trial 331-10-236 may remain on propranolol. Trial sites should only utilize medications that are approved for these indications in their respective countries.

Benzodiazepines, non-benzodiazepine sleep aids, anticholinergics, and propranolol must not be administered within 12 hours prior to scheduled efficacy and safety assessments, including EPS scales. Investigators are encouraged to delay scale administration until 12 hours have elapsed, if at all possible. However, if delaying administration of efficacy and safety scales is not feasible, the scales should still be administered and the use of the medication documented, including a notation of the drug name, dose, and time of administration on the eSource.

The subject's best medical interests should guide the investigator in the management of conditions that are pre-existing or that develop during the trial (intercurrent illness or AEs). The investigator should examine the acceptability of all concomitant medications not explicitly prohibited. In order to ensure that appropriate concomitant therapy is administered, it is essential that subjects be instructed not to take any medications (either self-administered non-prescription drugs or prescription therapy prescribed by another physician) without prior consultation with the investigator. All trial personnel should be familiar with the content of the IB for brexpiprazole in order to manage the subject's condition adequately and select appropriate concomitant medications, if needed.

#### **4.2.2 Non-therapy Precautions and Restrictions**

##### **4.2.2.1 Precautions**

Subjects should not undergo any elective medical procedure without prior consultation with the investigator. An elective procedure (minor surgery, dental surgery, orthopedic surgery, etc) that might require hospitalization or general anesthesia should be deferred until after the trial whenever clinically appropriate.

##### **4.2.2.2 Restrictions**

With the exception of inpatient group therapy and outpatient group therapy, new-onset psychotherapy is prohibited during the trial. In other words, except for inpatient and outpatient group therapies, subjects may only receive psychotherapy (eg, individual, group, marriage, or family therapy) if they have been participating in the therapy regularly (ie, weekly) for at least 6 weeks (42 days) prior to screening/baseline and commit to maintain their participation during the course of the trial at the current frequency or unless permission is obtained from the medical monitor.

Consumption of grapefruit, grapefruit products, Seville oranges, or Seville orange products within 72 hours prior to dosing and during the trial is prohibited. Subjects will be instructed to refrain from drinking alcoholic beverages or using illicit drugs during participation in the trial. The investigator may request a blood or urine drug screen at any time during the trial if there is a suspicion of illicit drug use.

## 5 Reporting of Adverse Events

### 5.1 Definitions

An AE is defined as any untoward medical occurrence in a patient or clinical trial subject administered a medicinal product and which does not necessarily have a causal relationship with this treatment. AEs would not include information recorded as medical history at Trial 331-10-234 End of Treatment or pre-planned procedures for which the underlying condition was known and no worsening occurred. An adverse reaction is any untoward and unintended response to an IMP related to any dose administered.

A suspected adverse reaction is any AE for which there is a reasonable possibility that the IMP caused the AE. For the purpose of IND safety reporting, “reasonable possibility” means there is evidence to suggest a causal relationship between the IMP and the AE. Suspected adverse reaction implies a lesser degree of certainty about causality.

A serious adverse event (SAE) includes any event that results in any of the following outcomes:

- Death
- Life-threatening; ie, the subject was, in the opinion of the investigator, at immediate risk of death from the event as it occurred. It does not include an event that, had it occurred in a more severe form, might have caused death.
- Persistent or significant incapacity/disability or substantial disruption of the ability to conduct normal life functions.
- Requires inpatient hospitalization or prolongs hospitalization.
  - Hospitalization itself should not be reported as an SAE; whenever possible the reason for the hospitalization should be reported.
  - Hospitalizations or prolonged hospitalizations for social admissions (ie, those required for reasons of convenience or other non-medical need) are not considered SAEs.
- Congenital anomaly/birth defect.

- Other medically significant events that, based upon appropriate medical judgment, may jeopardize the subject and may require medical or surgical intervention to prevent one of the outcomes listed above; eg, allergic bronchospasm requiring intensive treatment in an emergency room or home, blood dyscrasias or convulsions that do not result in hospitalization, or the development of drug dependency or drug abuse.

Nonserious adverse events are all AEs that do not meet the criteria for a “serious” AE.

If a subject is experiencing an EPS, the specific EPS must be indicated on the AE page of the eSource. Examples of AEs that are considered EPS include, but are not limited to: generalized rigidity, hyperkinesia, bradykinesia, akinesia, dystonia, hypertonia, akathisia, tremor, flexed posture, involuntary muscle contractions, athetosis, and chorea. If a subject is experiencing 2 or more of these symptoms, whether or not treatment with an anticholinergic is required, this is considered as extrapyramidal syndrome and must be entered as “extrapyramidal syndrome” on the AE page of the eSource instead of the individual symptoms. Permitted treatments for EPS are described in [Section 4.2.1](#).

Immediately Reportable Event (IRE):

- Any SAE.
- Any AE related to occupational exposure.
- Potential serious hepatotoxicity cases (any increase of AST or ALT  $\geq$  3 times the upper normal limit or screening value with an increase in total bilirubin  $\geq$  2 times the upper normal limit or screening value)
- Pregnancies are also defined as IREs. Although normal pregnancy is not an AE, it will mandate IMP discontinuation and must be reported on an IRE form to the sponsor. Pregnancy will only be documented on the AE CRF if there is an abnormality or complication.

Clinical Laboratory Test Value Changes: It is the investigator’s responsibility to review the results of all laboratory tests as they become available. This review will be documented by the investigator’s dated signature on the laboratory report. For each abnormal laboratory test result, the investigator needs to ascertain if this is an abnormal (ie, clinically significant) change from baseline for that individual subject. This determination, however, does not necessarily need to be made the first time an abnormal value is observed. The investigator may repeat the laboratory test or request additional tests to verify the results of the original laboratory tests. If this laboratory value is considered medically relevant by the investigator (subject is symptomatic, requiring

corrective treatment or further evaluation), or if the laboratory value leads to discontinuation, or fulfills a seriousness criterion, this is considered an AE.

Severity: Adverse events will be graded on a 3-point scale and reported as indicated on the CRF. The intensity of an adverse experience is defined as follows:

- 1 = Mild:** Discomfort noticed, but no disruption to daily activity.
- 2 = Moderate:** Discomfort sufficient to reduce or affect normal daily activity.
- 3 = Severe:** Inability to work or perform normal daily activity.

IMP Causality: Assessment of causal relationship of an AE to the use of the IMP is defined as follows:

- Related:** There is a reasonable possibility of a temporal and causal relationship between the IMP and the AE.
- Not Related:** There is no temporal or causal relationship between the IMP and the AE.

## 5.2 Eliciting and Reporting Adverse Events

The investigator will periodically assess subjects for the occurrence of AEs. To avoid bias in eliciting AEs, subjects should be asked the non-leading question: “How have you felt since your last visit?” All AEs (serious and nonserious) reported by the subject must be recorded on the source documents and CRFs provided by the sponsor. Adverse event collection is to begin after a subject has signed the ICF.

Use medical terminology in AE reporting. Adverse events should be reported as a single unifying diagnosis whenever possible or, in the absence of a unifying diagnosis, as individual signs or symptoms. Exacerbation or disease progression should be reported as an AE only if there are unusual or severe clinical features that were not present, or experienced earlier, or not expected based on the course of the condition. A reported AE that undergoes a change in severity, seriousness, or toxicity should be reported as a new AE on the eSource.

Note: Normal pregnancy is not an AE and should not be recorded on the eSource; guidelines outlined in [Section 5.5](#) should be followed for pregnancy reporting.

In addition, the sponsor must be notified immediately by telephone, fax, or e-mail of any IREs according to the procedure outlined below, in [Section 5.3](#). Special attention should be paid to recording hospitalization and concomitant medications.

### **5.3      Immediately Reportable Events**

The investigator must immediately report after either the investigator or site personnel become aware of any SAE, potential serious hepatotoxicity, or confirmed pregnancy, by telephone, fax, or e-mail to the sponsor using the contact information on the cover page of this protocol. An IRE form must be completed and sent by e-mail, fax, or overnight courier to the sponsor. (Please note that the IRE form is NOT the AE screen in eSource.)

Subjects experiencing SAEs should be followed clinically until their health has returned to baseline status, or until all parameters have returned to normal or have otherwise been explained. It is expected that the investigator will provide or arrange appropriate supportive care for the subject and will provide prompt updates on the subject's status to the sponsor.

### **5.4      Potential Serious Hepatotoxicity**

For a subject who experiences an elevation in AST or ALT that is  $\geq 3$  times the ULN, a total bilirubin level should also be evaluated. If the total bilirubin is  $\geq 2$  times the ULN, complete an IRE form with all values listed and also report as an AE on the eSource.

### **5.5      Pregnancy**

For females and for men who are sexually active, there must be a documented agreement that the subject and their partner will take effective measures (ie, double-barrier method) to prevent pregnancy during the course of the trial and for 30 days after the last dose of IMP. Unless the subject is sterile (ie, females who have had a bilateral oophorectomy or hysterectomy or who have been postmenopausal for at least 12 consecutive months; or men who have had a bilateral orchidectomy) or remains abstinent, 2 of the following precautions must be used: vasectomy, tubal ligation, vaginal diaphragm, intrauterine device, birth control pills, birth control depot injection, birth control implant, birth control patch, condom with spermicide, or sponge with spermicide. Any single method of birth control, including vasectomy and tubal ligation, may fail, leading to pregnancy. The contraceptive method will be documented at each trial visit.

Before enrolling females in this clinical trial, investigators must review the below guidelines about trial participation with all females. The topics should generally include:

- General information
- Informed consent form
- Pregnancy prevention information
- Drug interactions with hormonal contraceptives
- Contraceptives in current use
- Guidelines for the follow-up of a reported pregnancy

Before trial enrollment, females must be advised of the importance of avoiding pregnancy during trial participation and the potential risk factors for an unintentional pregnancy. The subject must sign an informed consent form stating that the above-mentioned risk factors and the consequences were discussed with her.

A urine or serum pregnancy test for human chorionic gonadotropin (hCG) will be performed at screening on all females. If a urine test is performed and is positive, the investigator will follow up with a confirmatory serum test.

During the trial, all females should be instructed to contact the investigator immediately if they suspect they might be pregnant (eg, missed or late menstrual cycle).

If a subject is suspected to be pregnant before she receives IMP, the IMP administration must be withheld until the results of serum pregnancy tests are available. If the pregnancy is confirmed, the subject must not receive the IMP and must not be enrolled in the trial. If pregnancy is suspected while the subject is taking IMP, the IMP must be withheld immediately (if reasonable, taking into consideration any potential withdrawal risks) until the result of the pregnancy test is known. If pregnancy is confirmed, the IMP will be permanently discontinued in an appropriate manner (eg, dose tapering if necessary for subject safety) and the subject will be withdrawn from the trial. Exceptions to trial discontinuation may be considered for life-threatening conditions only after consultations with the Clinical Safety and Pharmacovigilance department (see the cover page of this protocol for contact information).

The investigator must immediately notify the sponsor of any pregnancy associated with IMP exposure during the trial and for 30 days after the last dose of IMP, and record the event on the IRE form and forward it to the sponsor. The sponsor will forward Pregnancy Surveillance Form(s) for monitoring the outcome of the pregnancy.

Protocol-required procedures for trial discontinuation and follow-up must be performed on the subject unless contraindicated by pregnancy (eg, x-ray studies). Other appropriate pregnancy follow-up procedures should be considered, if indicated. In addition, the investigator must report to the sponsor, on appropriate Pregnancy Surveillance Form(s), follow-up information regarding the course of the pregnancy, including perinatal and neonatal outcome. Infants will be followed for a minimum of 6 months from the date of birth. Local regulatory requirements must be followed for follow-up and reporting on pregnancy cases and infants.

## **5.6 Procedure for Breaking the Blind**

Not applicable; this is an open-label trial.

## **5.7 Follow-up of Adverse Events**

For this trial, information on AEs will be followed for up to 21 ( $\pm 2$ ) days after the last dose of IMP has been administered.

### **5.7.1 Follow-up of Nonserious Adverse Events**

Nonserious AEs that are identified at any time during the trial must be recorded on the AE eSource with the current status noted. All nonserious events that are ongoing at the last scheduled contact will be recorded as ongoing on the eSource. For any AE having been identified throughout the trial, during analysis, additional relevant medical history information may be requested to further ascertain causality (including, but not limited to, information such as risk-related behavior, family history and occupation).

### **5.7.2 Follow-up of Serious Adverse Events**

This trial requires that subjects be actively monitored for SAEs up to 21 ( $\pm 2$ ) days after the last dose of IMP is administered.

Serious AEs that are **identified or ongoing at the last scheduled contact** must be recorded on the AE CRF page and reported to the sponsor according to the reporting procedures outlined in [Section 5.3](#). This may include **unresolved previously reported SAEs, or new SAEs**. The investigator will follow SAEs until the events are resolved, stabilized, or the subject is lost to follow-up. Resolution means that the subject has returned to the baseline state of health and stabilized means that the investigator does not expect any further improvement or worsening of the subject's condition. The investigator will continue to report any significant follow-up information to the sponsor up to the point the event has been resolved.

### **5.7.3 Follow-up and Reporting of Serious Adverse Events Occurring after Last Scheduled Contact**

Any new SAEs reported by the subject to the investigator that occur **after the last scheduled contact**, and are determined by the investigator to be reasonably associated with the use of the IMP, should be reported to the sponsor. This may include SAEs that are captured on follow-up telephone contact or at any other time point after the defined trial period (ie, up to last scheduled contact). The investigator should follow SAEs identified after the last scheduled contact until the events are resolved, stabilized, or the subject is lost to follow-up. The investigator should continue to report any significant follow-up information to the sponsor up to the point the event has been resolved or stabilized.

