#### Rollover Subjects from Trial 331-10-234

*Screening/Baseline:* Subjects will be assessed for eligibility at the last visit of the double-blind trial (ie, Week 6 visit of Trial 331-10-234). Subjects or their parent/legal guardian will complete a separate ICF and subjects will provide assent as required for participation in Trial 331-10-236 before any procedures specific to the open-label trial are performed. The assessments from the last visit of the double-blind trial will serve as the baseline measures for Trial 331-10-236 for any assessment that is not unique to the open-label trial. Medical history will be updated, if necessary.

*Open-label Treatment:* Eligible subjects from Trial 331-10-234 will receive daily treatment with open-label brexpiprazole in the open-label treatment period of Trial 331-10-236 as described in [Section 3.2.1](#).

*Follow-up:* Subjects will be followed up for safety via telephone contact or clinic visit 21 ( $\pm$  2) days after the last dose of IMP.

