### **3.7.1.3 Follow-up**

All subjects (rollover and de novo completers as well as premature withdrawals from either the conversion period or open-label treatment period) will be followed up either by telephone or other acceptable means of contact 21 ( $\pm$  2) days after the last dose of IMP to assess any new or ongoing AEs and to record any concomitant medications. Depending upon the type of follow-up required, other evaluations or tests may be conducted or performed.

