### **3.7.4      End of Trial**

The end of trial date is defined as the last date of contact or the date of final contact attempt from the post-treatment follow-up eSource page for the last subject completing or withdrawing from the trial.

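### Protocol 5.7.3 places the follow-up telephone contact after the trial period and attaches a causality condition to SAEs found there, while the rest of the protocol makes it a scheduled in-trial contact with all SAEs captured; the last scheduled contact is never defined.

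*Protocol*

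**What the plan says.** Protocol 5.7.2 sets the unconditional rule: "This trial requires that subjects be actively monitored for SAEs up to 21", a figure in days counted from the last dose with a tolerance of 2. At the last scheduled contact, SAEs whether new or unresolved fall under this instruction: "must be recorded on the AE CRF page and reported to the sponsor according to the reporting procedures outlined in" (the cross-reference is to 5.3). No causality test is attached.

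Protocol 5.7.3 sets the conditional rule. For new SAEs that arise after the last scheduled contact, the condition reads: "and are determined by the investigator to be reasonably associated with the use of the IMP, should be reported to the sponsor". The next sentence gives the example: "This may include SAEs that are captured on follow-up telephone contact or at any other time point after the defined trial period". A parenthesis then equates the trial period with the time up to the last scheduled contact, a term the protocol does not define.

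The follow-up call itself is described elsewhere, each time at the same 21 (± 2)-day point:
- Section 3.1, for rollover subjects and in the same terms for de novo subjects: "Subjects will be followed up for safety via telephone contact or clinic visit 21".
- Section 3.7.1.3, for completers and early withdrawals alike: "will be followed up either by telephone or other acceptable means of contact 21". The purpose given is to assess new and ongoing AEs.
- Tables 3.7-1 and 3.7-2: a follow-up column with the AE row marked.
- Section 3.7.4, which dates the end of the trial by its final subject: "the last date of contact or the date of final contact attempt from the post-treatment follow-up eSource page".

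Serious TEAEs are among the primary endpoints (Protocol 3.5.1). SAP 8.1 tabulates serious TEAEs without a causality restriction, and SAP 8.1.1 takes AEs into the tables up to 30 days after the last open-label dose.

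**The concern.** The same call is treated in two ways. Under 5.7.2, read with 3.7.1.3 and the schedules, an SAE heard on it is recorded and reported whatever its cause. Under the example in 5.7.3, an SAE heard on it belongs to the group reported only if the investigator ties it to the drug. No rule says which section prevails, and 5.7.3 is the one that names the call in connection with SAEs.

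At stake is the completeness of a primary safety endpoint in the weeks after stopping drug. The SAP counts serious TEAEs there regardless of cause. A site that applied 5.7.3 would put an open-label judgement of relatedness ahead of the report. A site that applied 5.7.2 would not. The post-dose count could then read low and depend on which section each site follows. There is also an odd asymmetry: under 5.7.1 a nonserious AE heard on the call is recorded without any causality test, while an SAE heard on the same call might go unreported.

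**Working it through.** No power, alpha or sample-size figure bears on this point, and the plan gives no figure of its own to reproduce. The check sets the passages side by side and then counts days.

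**1. Is the call inside the trial, and is there a causality condition?**

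| Place in the protocol | Position of the call | Causality condition |
|---|---|---|
| 3.1, 3.7.1.3 | Planned, 21 (± 2) days after last dose | None |
| Tables 3.7-1, 3.7-2 | Scheduled column, AEs marked | None |
| 3.7.4 | Its eSource page dates the end of trial | Not applicable |
| 5.2 | Call not named; all AEs recorded | None |
| 5.3 | Call not named; any SAE reported immediately | None |
| 5.7.2 | Active SAE monitoring to 21 (± 2) days | None |
| 5.7.3 | Example of a time after the trial period | Yes |

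**2. What must the term mean for the 5.7.3 example to work?** The operative test in 5.7.3 is that the SAE occurs after the last scheduled contact. If that contact is the 21-day call, an SAE that began before the call fails the test. For an SAE captured on the call to qualify, the last scheduled contact has to be an earlier one, Month 24 or early termination. The condition would then cover the whole stretch from that visit to the call, which is the stretch 5.7.2 says is monitored without condition.

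**3. Days after last dose.** Inputs: contact at day 19 to 23 (21 ± 2, Protocol 3.7.1.3); AE tables to day 30 (SAP 8.1.1).
- Disputed between 5.7.2 and 5.7.3, last dose to contact: 19/30 = 63%, 21/30 = 70%, 23/30 = 77% of the 30-day window.
- Past scheduled collection: 30 − 23 = 7 days to 30 − 19 = 11 days (9 at day 21), or 23% to 37% of the window. Here SAEs arrive only passively, and the 5.7.3 condition applies under either reading.

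**4. Share of one subject's AE table window**, taken as treated days + 30. The treated durations are the SAP Table 10.2-1 target days for Month 24, Month 12, Month 6 and Week 4, used as illustrations.
- 744 days: 21/774 = 2.7%
- 372 days: 21/402 = 5.2%
- 186 days: 21/216 = 9.7%
- 28 days: 21/58 = 36%

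These are shares of time, not of events.

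**5. Order of magnitude, on assumptions only.** The documents give neither a post-treatment SAE rate nor the share judged unrelated.
- 350 × 21/365.25 = 20.1 person-years. SAP Section 4 expects fewer than 350 subjects, so this is an upper figure.
- Assumed 5 to 20 SAEs per 100 person-years: 1.0 to 4.0 SAEs.
- Assumed 50% to 90% judged unrelated: 0.5 to 3.6 SAEs, and only if every site followed 5.7.3.
- On the same constant rate and an assumed mean exposure of one year, the window is 20.1/(350 + 20.1) = 5.4% of person-time. The loss is then 0.5 × 5.4% to 0.9 × 5.4%, about 3% to 5% of SAEs.

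**The case against.** A reader might infer that part of the serious-TEAE endpoint is filtered by causality as the protocol stands. The documents do not support that. Sections 3.7.1.3, 5.2, 5.3 and 5.7.2 and the schedules all call for unconditional capture, so one illustrative sentence would have to override them all. Section 5.7.3 also governs reporting to the sponsor and nowhere says that an unrelated SAE may be left off the AE page. The supportable statement is that filtering could happen, and unevenly.

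The onset argument is the strongest reply. If the 21-day call is the last scheduled contact, 5.7.3 does not reach SAEs that began before it. That is right once the term is defined, but it is not defined, and on that meaning the example in 5.7.3 misfires.

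The example could instead refer to a later, unscheduled call, since SAEs are followed until resolved or stable and 3.8.3.4 mentions telephone contact as a form of follow-up. That reading is possible but less natural, because 3.1 uses the same term for the planned safety follow-up.

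Two further inferences should be resisted. One sets 0.5 to 3.6 lost SAEs against about 7 subjects, the adult program's 91/4488 = 2.0% applied to 350, and concludes that up to half could be missed. That program pools completed trials that include phase 1 studies in healthy subjects (Protocol 1.3), so it is no yardstick for 24 months of treatment in adolescents. The other uses relapse admissions as the typical lost event. Section 5.2 already restricts when an exacerbation counts as an AE, and 5.1 asks for the reason for an admission rather than the admission itself, whatever 5.7.3 says.

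**Conclusion.** The contradiction is real and should be reconciled: 5.7.3 places the follow-up telephone contact after the trial period under a causality condition, every description of the planned 21 (± 2)-day call places it inside the trial without one, and the term that would settle the matter is undefined. The consequence is a possibility, not an established loss. It depends on some sites letting 5.7.3 prevail and treating non-reporting to the sponsor as non-recording.

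The likely number of events is small and cannot be estimated from the documents; the event counts above rest wholly on assumed rates. The disputed time is about 3% of the AE table window for a subject treated for 744 days and about a third for one treated for 28 days, so any effect would fall mainly on early terminators.

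A separate mismatch does not depend on how the conflict is read. The SAP tables run 7 to 11 days beyond scheduled collection, and SAEs in that span come in only passively and under the 5.7.3 condition. The introduction to SAP Section 8 describes the AE summary period as treatment plus a 21-day follow-up, so the SAP itself gives two windows.

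**What to change.** In the protocol:
- Define the last scheduled contact in 5.7 as the 21 (± 2)-day follow-up contact. Where the schedule footnotes waive that contact because the early termination visit came later than this after the last dose, the definition should name that visit.
- Delete the reference to the follow-up telephone contact from the example in 5.7.3.
- State that every SAE with onset up to that contact is recorded in eSource and reported under 5.7.2 regardless of causality. The association condition then applies only to SAEs with onset after it.

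In the SAP:
- Note in 8.1.1 that the 30-day window extends 7 to 11 days past scheduled collection and that SAEs in that span are captured only passively and under the 5.7.3 condition. Reconcile this with the 21-day period in the introduction to Section 8.

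The cost is a short wording clarification, a memo to sites and a line in the SAP. No visits or assessments are added, because the call already takes place.
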